10.3.2 Subjective Effects Measures

Where applicable, responses to the questionnaires recorded as VAS scores or Likert scales will be treated as continuous variables and summarized descriptively by study product and time point for each questionnaire item using means, standard deviations (SD), medians, and ranges.

The PES will be considered as a 7-point scale. Responses will be presented as the following factor scores:

- a) Satisfaction: average of the response scores from Questions 1, 2, 3, and 12;
- b) Psychological reward: average of the response scores from Questions 4 to 8;
- c) Aversion: average of the response scores from Questions 9, 10, 16, and 18;
- d) Relief: average of Questions 11, 13, 14, 15, and reversed for Question 20 (i.e., not at all = 7, extremely = 1);
- e) Questions 17, 19, 21 will be summarized as individual item scores.

The maximum response (E_{max}) and time to maximum response (TE_{max}) will be determined for the Urge to Smoke questionnaire.

Responses and parameters will be listed by subject and summarized by study product using descriptive statistics.

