1.2 Study Purpose

This study is being conducted to assess the abuse liability and puffing topography of blu disposable e-cigarettes in adult combustible cigarette smokers. Nicotine uptake, subjective effects, and puff topography will be evaluated and compared with subjects’ usual brand combustible cigarette. It is anticipated that the results from this study will provide evidence that the blu disposable e-cigarettes relative to subjects’ usual brand combustible cigarettes are appropriate for the protection of the public health, and will therefore support a Premarket Tobacco Product Application (PMTA) submission to the Center for Tobacco Products (CTP) at the Food and Drug Administration (FDA). The FDA’s PMTA guidance for ENDS (FDA 2019) suggests that applicants include, in addition to other information, results from studies addressing topography and use patterns and an assessment of abuse liability.

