2. STUDY OBJECTIVES AND ENDPOINTS

2.1 Study Objectives

Primary objectives:

- To determine the PK of nicotine absorption into the blood of subjects when they use the blu disposable e-cigarette with varying flavors in each study arm compared to when they smoke a combustible cigarette.
- To characterize subjective effects after use of the study products and a combustible cigarette.

Secondary objectives:

- To compare puff topography when subjects smoke a combustible cigarette versus use of the blu disposable e-cigarette.
- To evaluate overall safety in subjects using the blu disposable e-cigarette.

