2.2 Study Endpoints

Primary endpoints:

- Baseline-adjusted plasma nicotine $C_{max,0-120}$, $C_{avg,0-120}$, $T_{max,0-120}$, AUC_{0-120} , $C_{max,120-180}$, $T_{max,120-180}$, $AUC_{120-180}$, $C_{avg,120-180}$, AUC_{0-180}
- Ratio of $C_{max,120-180}/C_{max,0-120}$
- Ratio of $C_{avg,120-180}/C_{avg,0-120}$
- Subjective effects measures:
 - Product liking assessment
 - Intent to Use Product Again assessment
 - Urge to Smoke Questionnaire
 - Product Evaluation Scale (PES)
- Mass change of blu disposable e-cigarettes during puffing

Secondary endpoints:

- Puff topography (e.g., count, duration, volume, flow rate, and inter-puff interval)

Safety endpoints:

- Heart rate and blood pressure during product use sessions
- Adverse events (AE)/Serious adverse events (SAE)

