### **7.2. SUMMARY STATISTICS**

Continuous variables will be summarized using descriptive statistics including number of subjects, mean, median, standard deviation (SD), minimum and maximum values of the raw data, coefficient of variance (CV; PK concentration and PK parameters), geometric mean, and geometric CV (%) (PK parameters only). Means and medians will be reported to one more significant digit than the raw data values being analyzed. Standard deviations will be reported to two more significant digits, and the minimum and maximum will be reported to the same number of significant digits as the raw data values being analyzed.

Categorical variables will be summarized as the number and percentage of subjects per category. All percentages will be rounded to one decimal point. To ensure completeness, all summaries for categorical and discrete variables will include all categories, even if none of the subjects had a response in a particular category. Denominators for each analysis will be based on the population of interest (e.g., Safety Population; subjects with non-missing data) unless otherwise noted.

In general, all data will be listed by subject and time point.

SAS software (version 9.3 or higher, Cary, NC) will be used for data presentation and summarization including summary tables, graphs, and data listings not associated with the nicotine concentration or PK parameters.

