### 8.7. SUBJECTIVE MEASURES

Response to product liking, urge to smoke, and intent to use product again questionnaires are recorded as VAS scores or Likert scales and will be treated as continuous variables.

The PES is considered as a 7-point scale. Responses will be presented as the following factor scores:

- Satisfaction: average of the response scores from Questions 1, 2, 3, and 12;
- Psychological reward: average of the response scores from Questions 4 to 8;
- Aversion: average of the response scores from Questions 9, 10, 16, and 18;
- Relief: average of Questions 11, 13, 14, 15, and reversed for Questions 20 (i.e., not at all = 7, extremely = 1);
- Questions 17, 19, & 21 will be summarized as individual item scores.

Statistical Analysis Plan  
Protocol No.: Fontem-PK-01

For the Urge to Smoke questionnaire, the maximum response (Emax), defined as the maximum absolute value of change from baseline and time to maximum response (TEmax) will be determined. In the case of multiple values considered as Emax, the earliest time point associated will be used in calculating TEmax.

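### For the primary subjective endpoints, no within-subject difference from the usual-brand cigarette, with a confidence interval, is pre-specified

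*Protocol*

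**What the plan says.** Protocol 1.2 describes the aim this way: "Nicotine uptake, subjective effects, and puff topography will be evaluated and compared with" the usual-brand cigarette. SAP 3.1 repeats the sentence. The formal primary objective in Protocol 2.1 is milder: "To characterize subjective effects after use of the study products and a combustible cigarette". SAP 3.2.1 carries the same wording. Protocol 2.2 lists "Subjective effects measures" among the primary endpoints, namely Product Liking, Intent to Use Product Again, Urge to Smoke and the Product Evaluation Scale (PES). SAP 3.3.1 does likewise.

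Under Protocol 10.3.2 the responses are "summarized descriptively by study product and time point for each questionnaire item using means, standard deviations (SD), medians, and ranges". PES items are averaged into four factor scores, and a maximum response is derived for Urge to Smoke. The section closes: "Responses and parameters will be listed by subject and summarized by study product using descriptive statistics".

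SAP 8.7 says that the Product Liking, Urge to Smoke and Intent to Use responses "are recorded as VAS scores or Likert scales and will be treated as continuous variables", repeats the PES factors, and adds a definition of the Urge to Smoke maximum response, "defined as the maximum absolute value of change from baseline and time to maximum response (TEmax) will be determined". The general rule in SAP 7.2 is: "Continuous variables will be summarized using descriptive statistics including number of subjects, mean, median, standard deviation (SD), minimum and maximum values". For PK it adds coefficients of variation and geometric means. It names no confidence interval.

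The only planned contrast with the cigarette is the analysis of variance with Dunnett comparisons on Cmax0-120 and AUC0-120 (Protocol 10.3.1, SAP 8.9). The only intervals mentioned are those for mean plasma nicotine by product (Protocol 10.3.1). SAP 9 records no changes to the planned analyses.

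**The concern.** How much the e-cigarettes are liked, wanted again, or relieve the urge to smoke, relative to the subject's own cigarette, is central to an abuse-liability assessment. The documents say the results should support a tobacco product application. The design suits that question: each subject is meant to use and rate all six products, so each is their own reference.

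The planned tables do not use this. A by-product SD correctly describes spread under one product, but it carries no information on how a subject's e-cigarette score moves with the same subject's cigarette score. The SD of the paired difference cannot be derived from six separate means and SDs. The tables would let a reader subtract two means, but would give neither the within-subject difference nor its precision.

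There is a second, smaller problem. Missing values are not imputed and denominators shrink (Protocol 10.3, SAP 7.3.1), and dropouts after Visit 2 may be replaced (Protocol 5.2). The product means may therefore rest on partly different subjects.

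If differences are wanted later, their form would be chosen after open-label data have been seen.

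**Working it through.** **Is a contrast planned anywhere?** The places where one could appear:

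| Place | What it gives for subjective scores |
|---|---|
| Protocol 10.3.2 | mean, SD, median, range by product and time point; listings |
| SAP 8.7 | continuous scoring, PES factors, Emax and TEmax |
| SAP 7.2 | n, mean, median, SD, minimum, maximum |
| Protocol 10.3.1, SAP 8.9 | contrast with the cigarette for two PK parameters only |
| SAP 9 | no changes |

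Emax for Urge to Smoke is a within-subject quantity, but it is a change from baseline within one visit. It does not set one product against another. No paired contrast is planned.

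**Scale of the missing quantity.** The documents give n = 20 (Protocol 10.1) and no power calculation, SD, correlation or effect size for these endpoints, so there is no figure of the plan to reproduce. The following are assumptions: a common SD of 25 points per product, a correlation r of 0.3, 0.5 or 0.7 between a subject's scores on two products, and complete data.

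- Unpaired, all that can be rebuilt from printed SDs: t(0.975, 38) × SD × √(2/20) = 2.024 × 25 × 0.3162 = 16.0.
- Paired, unadjusted: t(0.975, 19) × SD × √(2(1−r)/20), with t = 2.093.
- Paired, Dunnett-adjusted for five contrasts: the same formula with a simulated critical value of about 2.55 on (20−1) × (6−1) = 95 degrees of freedom.

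| r | Paired, unadjusted: SD units | at SD 25 | Dunnett-adjusted: SD units | at SD 25 |
|---|---|---|---|---|
| 0.3 | 0.554 | 13.8 | 0.675 | 16.9 |
| 0.5 | 0.468 | 11.7 | 0.570 | 14.3 |
| 0.7 | 0.363 | 9.1 | 0.442 | 11.0 |

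Like must be compared with like. The 16.0 is unadjusted and belongs beside 13.8, 11.7 and 9.1. At r = 0 the unadjusted paired value is 16.5, so pairing then gains nothing. For the adjusted column, the matching no-pairing value is the same formula at r = 0: 2.55 × 25 × √(2/20) = 20.2.

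All values scale with the SD. At r = 0.5 the unadjusted paired half-width is 9.4 for an SD of 20 and 14.0 for an SD of 30, against unpaired values of 12.8 and 19.2.

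**The case against.** The strongest reply is that the formal objective asks only for characterization, while the same list of objectives uses comparative language for PK and topography. By-product description meets an objective so worded, in a Phase I study without a power calculation. This stands, and it limits the point: the comparison comes from the study purpose narrative, which names no estimate, test or interval. But the narrative appears in both documents and the questionnaires are primary endpoints. A small unpowered study is also where intervals help most.

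A reader might infer that the study is unable to attach any uncertainty to the comparison. The documents do not support that. Printed SDs allow an unpaired interval, by-subject listings allow paired differences to be derived, Protocol 10 lets the SAP add analyses, and SAP 2 provides for reporting deviations. The uncertainty is unplanned, not unobtainable.

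A reader might also infer that a paired interval would settle how the e-cigarettes compare with the cigarette. It would not. The cigarette is always used at Visit 2 and only the order at Visits 3 to 7 is randomized (Protocol 3.1 and 6), without blinding. Every contrast with the cigarette is confounded with visit order, and an interval covers sampling error only. Subtracting means by eye has the same defect.

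Last, scores for a usual brand among established smokers may sit near the end of a bounded scale, where a common-variance model may fit poorly. That is a fair caution, and the fix allows for it.

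**Conclusion.** The point holds as a gap in pre-specification. Both documents state a comparison of subjective effects with the usual-brand cigarette and make the measures primary endpoints, yet neither plans a within-subject difference or an interval for them. It is an inexpensive improvement that should be made. It is not a flaw that invalidates the study, and the softer wording of the formal objective weighs against grading it higher.

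The conclusion rests on the text alone. The half-widths depend on an assumed SD, assumed correlations and complete data, and show scale only. On a matched adjusted basis, pairing multiplies the half-width by √(1−r), which is 0.84, 0.71 and 0.55 at correlations of 0.3, 0.5 and 0.7.

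**What to change.** In SAP 8.7, for Product Liking, Intent to Use Product Again, Urge to Smoke Emax and the four PES factor scores:

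- Name the model: product (six levels) as a fixed effect and subject as a random effect. Do not refer to the PK model, because Protocol 10.3.1 and SAP 8.9 leave that as one-way or repeated measures, and a one-way analysis would ignore the pairing.
- Report each e-cigarette-minus-cigarette difference with a Dunnett-adjusted 95% confidence interval, labelled as estimation with no success criterion.
- State with the results that the cigarette is always at Visit 2, so the contrasts are confounded with visit order and the intervals cover sampling error only.
- Because the scales are bounded, add a simple paired check such as the median paired difference, with the number of pairs.

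Record the addition in SAP 9. Protocol 10 permits added analyses, but it also requires an amendment for major changes to the analysis of primary endpoints, so the sponsor should document which applies.

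The cost is one more set of tables from data already being collected, with no change to visits, procedures or sample size. The downside is more to interpret: seven outcomes × five contrasts = 35 intervals, with the Dunnett adjustment acting within each outcome and not across the seven.

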10.3.3 Puff Topography

The following topography parameters will be assessed:

- Puff duration
- Puff volume
- Peak puff flow rate
- Average puff flow rate
- Inter-puff interval

Summary statistics of puff topography parameters will be presented, including means, SD, medians, and ranges.

10.3.4 Mass Loss

The difference in weights before and after each product use session will be summarized by study product using descriptive statistics.

10.3.5 Safety

All clinical safety data will be summarized by subject and time point as appropriate.

All AEs captured in the database will be listed in by-subject data listings. However, only study product use-emergent AEs will be summarized. A study product use-emergent AE is defined as an AE that is starting or worsening at the time of or after the first study product use.

Frequencies of subjects with study product use-emergent AEs, regardless of relationship to study product, will be summarized and sorted by system organ class. Frequencies of subjects with study product use-emergent serious AEs will be likewise summarized. Frequencies of study product use-emergent AEs will be summarized by severity and relationship to study product.

All concomitant medications recorded will be listed by subject.

11. STUDY ADMINISTRATION

11.1 Ethics

11.1.1 Institutional Review Board

This protocol will be reviewed by the Advarra IRB, and the study will not start until the IRB has approved the protocol or a modification thereof. The IRB is constituted and operates in accordance with the principles and requirements described in the US Code of Federal Regulations (21 CFR Part 56). The IRB is compliant to International Council for Harmonisation (ICH) guidelines, and may be reached at:

Advarra IRB
[name]
[name]
[contact]

11.1.2 Ethical Conduct of the Study

This research will be carried out in accordance with the protocol, US Code of Federal Regulations, 21 CFR Parts 50, 56, and 312, the ethical principles set forth in the Declaration of Helsinki, GCP, and the ICH harmonized tripartite guideline regarding GCP (E6 Consolidated Guidance, April 1996).

11.1.3 Subject Information and Consent

The purpose of the study, the procedures to be carried out, and the potential hazards will be described to the subjects in non-technical terms. Subjects will be required to read, sign, and date an ICF summarizing the discussion prior to Screening and will be assured that they may withdraw from the study at any time without jeopardizing their medical care.

Subjects will be given a copy of their signed ICF.

11.2 Termination of the Study

The investigator reserves the right to terminate the study in the interest of subject welfare.

The sponsor reserves the right to suspend or terminate the study at any time.

11.3 Data Quality Assurance

Standard operating procedures are available for all activities performed at LA Clinical Trials, LLC relevant to the quality of this study. Designated personnel of LA Clinical Trials, LLC will be responsible for implementing and maintaining quality assurance (QA) and quality control systems to ensure that the study is conducted, and that data are generated, documented and reported in compliance with the study protocol, GCP and Good Laboratory Practice requirements as well as applicable regulatory requirements and local laws, rules and regulations relating to the conduct of the clinical study.

All clinical data will undergo a 100% quality control check prior to clinical database lock. Edit checks are then performed for appropriate databases as a validation routine using SAS® or comparable statistical program to check for missing data, data inconsistencies, data ranges, etc. Corrections will be made prior to database lock.

11.4 Direct Access to Source Data/Documents

LA Clinical Trials, LLC will ensure that the sponsor, IRB and inspection by domestic and foreign regulatory authorities will have direct access to all study-related sites, source data/documents, and reports for the purpose of monitoring and auditing (ICH[E6][R2] 5.1.2 & 6.10). In the event that other study-related monitoring should be done by other parties, they will be required to sign a confidentiality agreement prior to any monitoring and auditing.

11.4.1 Monitoring the Study

The responsible study monitor or sponsor's designee will contact and visit the investigator as necessary, and he/she will be allowed, upon request, to inspect and verify all records of the study (e.g., source document, ICFs, CRFs, regulatory documents) in a manner consistent with GCP and all other applicable state and federal law.

It will be the study monitor's responsibility to inspect the source documents to verify the adherence to the protocol and the completeness, consistency, and accuracy of the data being entered in the CRF. The monitor will verify that each subject has consented in writing prior to any study procedures being performed. Where the terms of the informed consent, GCP, and all other applicable state and federal law permit, the monitor should have access to laboratory test reports and other subject records needed to verify the entries on the CRF. The investigator (or his/her designee) agrees to cooperate with the monitor to ensure that any issues detected in the course of these monitoring visits are resolved.

In addition, the sponsor's internal auditors (or designee) and government inspectors may evaluate the study and must be allowed access to CRFs, source documents, and other study files.

The investigator must notify the sponsor (or designee) promptly of any inspections of the study or activities related to the study scheduled by regulatory authorities, allow the sponsor (or designee) to be present, and promptly forward copies of inspection reports to the sponsor (or designee).

11.5 Reporting for the Study

11.5.1 Case Report Forms

LA Clinical Trials, LLC standard CRFs will be supplied. CRFs are produced, stored electronically, and are available to the designated study team members. Each CRF is reviewed and signed by the investigator. The final signed CRFs are provided to the sponsor in the format as decided upon between LA Clinical Trials, LLC and the sponsor (e.g., compact disc, flash drive, secure file transfer protocol). This will be documented in the Data Management Plan (if applicable).

AEs will be coded using MedDRA®. Coding will be completed by qualified members of LA Clinical Trials, LLC staff.

11.5.2 Report Format

According to the ICH Harmonized Tripartite Guideline (Organization of the Common Technical Document for the Registration of Pharmaceuticals for Human Use M4 and the ICH M2 Expert Working Group), the final report will be written according to the ICH E3 Guideline (Structure and Content of Clinical Study Reports).

11.5.3 Record Keeping

All raw data generated in connection with this study, together with the original copy of the final report, will be retained by LA Clinical Trials, LLC until at least 5 years after the last approval of a marketing application in an ICH region and until there are no pending or contemplated marketing applications in an ICH region or at least 5 years have elapsed since the formal discontinuation of clinical development of the investigational product. These documents should be retained for a longer period, however, if required by the applicable regulatory requirements or by an agreement with the sponsor. It is the responsibility of the sponsor to inform the investigator/institution as to when these documents no longer need to be retained.

11.6 Confidentiality

All clinic sites and vendors will have signed confidentiality agreements with LA Clinical Trials, LLC. By signing this protocol, the investigator and LA Clinical Trials, LLC staff will regard all information provided by the sponsor and all information obtained during the course of the study as confidential.

Neither the clinic site nor LA Clinical Trials, LLC will supply to the sponsor any subject names, initials, date of birth (except year), or other personal identifiers in compliance with HIPAA 2015. All such information appearing on any study document must be redacted before a copy of the document is supplied to the sponsor. The photocopied government-issued ID to verify subject age will be kept separate from other source documentation and not provided to the sponsor. Study findings stored on a computer will be stored in accordance with local data protection laws. As required, in the case of an event

where medical expenses are the responsibility of the sponsor, personal information i.e., full name, social security details etc. may be released to the sponsor. The subjects will be informed during the consenting process that representatives of the sponsor, IRB, or regulatory authorities may inspect their medical records to verify the information collected, and that all personal information made available for inspection will be handled in the strictest confidence and in accordance with local data protection laws.

